**NCT number: 20210712**

**Date: 2020/08/17**

## **Study Protocol and Statistical Analysis Plan**

### ***Study population***

The program of “Two Cancer (breast and cervical cancer) Screening” has been launched in China since 2009 to provide free screening tests for millions of rural women aged 35-59 years (Ministry of Health of China and All-China Women’s Federation). This program has been expanded to all eligible women in both rural and urban areas as a basic public health service since 2019. Based on this program, we conducted a prospective cluster randomized controlled screening trial in Shanghai, China.

Eligible women were aged 35–70 years without a history of breast cancer, including in-situ cancer or other cancers in the previous five years, without serious cardiopulmonary insufficiency, liver or kidney insufficiency or other systemic diseases, and with life expectancy of more than five years.

### ***Definition of a cluster***

We define one district as a cluster. In 2021, Shanghai has jurisdictions over 16 municipal districts. The division of districts was obtained from field measured data and reference to relevant geographical maps, using human-computer interaction to carry out the vectorization of administrative division maps. Of above divisions, seven are urban areas and nine are suburban. The urban area covered an area of 20-40 square kilometers with a resident population of 600,000 to 1 000,000. The suburban district covered an area of 300-1200 square kilometers with a population of 500,000 to 3,200,000. At least 20,000 women aged 35 to 70 were included in each district.

### ***Randomization method***

Randomization was conducted by cluster, where districts rather than individuals were chosen as units of randomization. In order to avoid transfer between control and intervention cluster, urban levels were used as our strata. We then randomly selected one district out of seven urban areas as intervention cluster and another one out of nine suburban areas as control cluster.

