### ***Participants and intervention***

Two women and children's care centers from randomly selected two districts were the main study locations. Women in the intervention arm received AI-assisted ultrasound conducted by trained female primary health workers, while women in the control arm received routine ultrasound conducted by doctors from the Maternal and Child Health Hospital. Participants in both arms were eligible for further diagnostic evaluation and treatment at Fudan university Shanghai cancer center and women in both groups were offered access to obtain rapid treatment at the hospital. Recruitment was started in January 2021 and completed in December 2022. All participants were then followed up till the end of 2023. The database was sealed in January 2024 for analysis.

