#### ***Sample size calculation***

Sample size was primarily calculated by expected detection and incidence data from breast cancer. According to the positive detection rate of Asian women with suspicious breast cancer lesion (5/1000), 16,000 participants were required. Based on the reported data by Shanghai Center for Disease Control and Prevention in 2017, the age-specific incidence rate of breast cancer among women aged 35-69 in urban Shanghai was 125.75/100,000, so that 20 breast cancer cases were expected to be screened. Our previous breast cancer screening study showed that the early stage rate of screen-detected breast cancer reached 83%, predicting about 17 breast cancer at early stage would be diagnosed in this study. All this would meet the evaluation needs of endpoint indicators.

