#### ***Statistical analysis***

Numerical data were shown as means and standard deviation (SD) and categorical variables in percentages. Sensitivity was determined via dividing the numbers of true-positive screening by the numbers of true-positive and false-positive screening. Specificity was determined via dividing the numbers of true-negative screening by the numbers of true-negative and false-negative screening. To calculate 95% CIs, we did bootstrapping based on 5000 samples. The significance of the differences of incidences was assessed using Poisson regression. For categorical variables we used Fisher's exact test or likelihood-based  $\chi^2$  test.

All analyses were done with IBM SPSS (version 20).

This study was performed according to the guidelines of the Helsinki Declaration and was approved by the Medical Ethics Committee of Fudan University Shanghai Cancer Center (No. 2008223-22). Informed consent was obtained from all individual participants included in the study.

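### AI screening was tied to one urban district and routine screening to one suburban district, so the screening method was not randomised and the primary comparison cannot isolate AI

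*Combined protocol and SAP*

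**What the plan says.** - Study population gives the design: "we conducted a prospective cluster randomized controlled screening trial in Shanghai, China".
- Definition of a cluster fixes the unit: "We define one district as a cluster". Shanghai's 16 districts divide into seven urban and nine suburban.
- Randomization method explains the stratification: "In order to avoid transfer between control and intervention cluster, urban levels were used as our strata". It then describes the draw: the investigators "randomly selected one district out of seven urban areas as intervention cluster and another one out of nine suburban areas as control cluster".
- That there are only two districts is confirmed under Participants and intervention: "care centers from randomly selected two districts were the main study locations". It also states that trained primary health workers scanned the AI arm and hospital doctors scanned the control arm.
- Outcomes makes the difference in early breast cancer incidence between the two groups the primary endpoint.
- Statistical analysis gives the test: "The significance of the differences of incidences was assessed using Poisson regression". It names no covariate and no term for district.

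**The concern.** Stratified cluster randomisation places both arms in every stratum and lets chance assign the arm. Here each stratum holds one arm only, and the random step selects a district within an arm that is already fixed. That is random sampling of districts, not random allocation of the screening method.

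The primary rate ratio therefore compares one urban district with one suburban district. Differences in background incidence, age mix or earlier screening between them would be read as the effect of AI. The documents give reason to expect differences:

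- The district areas do not overlap (20–40 against 300–1200 square kilometres).
- The free screening programme began in 2009 for rural women and was widened to urban women only from 2019. Whether the suburban districts counted as rural is not stated, so this is a plausible route to unequal prior screening, not a demonstrated one.

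Recruiting more women in the same two districts does not help. It narrows the interval around a biased estimate. The design label promises a protection against confounding that the described allocation does not give.

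**Working it through.** **1. The allocation.** Possible district pairs: 7 × 9 = 63. Pairs with AI in a suburban district: 0. Pairs with control in an urban district: 0. The probability that the AI arm is urban is 1.

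**2. Degrees of freedom.** Two clusters minus two parameters (intercept and arm) leaves 2 − 2 = 0. A district term, a random district effect or cluster-robust errors cannot recover a between-district variance from one district per arm.

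**3. The plan's event counts (Sample size calculation).** 16,000 × 125.75/100,000 = 20.12, stated as 20. Then 20.12 × 0.83 = 16.70, stated as about 17. Both reproduce. The incidence used is an urban one: "in urban Shanghai was 125.75/100,000, so that 20 breast cancer cases were expected to be screened". No suburban rate appears anywhere, so nothing in the documents supports equal background rates.

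**4. Bias.** If the urban:suburban background ratio is R and AI has no effect, the expected rate ratio is R, whatever the sample size.

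**5. How often that bias would reach significance.** Assumptions not in the documents: equal person-time per arm, two-sided 5% test, no AI effect, and the values of R. Let X and Y be independent Poisson counts. All pairs (X, Y) are enumerated, and the test rejects if its statistic exceeds 3.84:

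- Likelihood ratio: 2[X ln(2X/(X+Y)) + Y ln(2Y/(X+Y))]
- Wald: (ln(X/Y))² / (1/X + 1/Y), with a zero count treated as no rejection

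Total fixed at 16.70 events; means are 16.70·R/(1+R) and 16.70/(1+R):

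| R | Mean events, urban v suburban | Likelihood ratio | Wald |
|---|---|---|---|
| 1.0 | 8.35 v 8.35 | 5.7% | 3.8% |
| 1.25 | 9.28 v 7.42 | 8.2% | 5.7% |
| 1.5 | 10.02 v 6.68 | 13.9% | 10.4% |
| 2.0 | 11.13 v 5.57 | 29.3% | 23.5% |

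Because 125.75 per 100,000 is an urban rate, a second version holds the urban arm at 8.35 events and sets the suburban arm to 8.35/R. For R = 1.25, 1.5 and 2.0 rejection is then 8.2%, 13.2% and 24.9% by likelihood ratio (Wald 5.1%, 8.1%, 14.9%).

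**6. More events make it worse.** With 80 events in total and R = 1.5 (48 v 32), rejection rises to 43.6% (Wald 42.6%). The 80 only shows the direction. It equals 16,000 × 5/1000, the plan's rate for suspicious lesions, and is not a forecast of early cancers.

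**7. Equal mean rates, but districts that vary.** Gamma-distributed district rates give negative binomial counts with mean 8.35 per arm. For an assumed between-district coefficient of variation of 0.1, 0.2 and 0.4, test size is 6.7%, 9.8% and 21.0% by likelihood ratio (Wald 4.5%, 6.9%, 15.7%). Size is therefore not inflated in every case.

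**The case against.** - **The sentence may be a compressed report.** An unreported step, such as a coin toss for which stratum received AI, is not logically excluded. No section describes one, though. It would rescue the word randomised but still leave one district per arm, with arm inseparable from district. What stands is that the sponsor should confirm what was done.
- **Separating the arms was meant to limit transfer.** That is a sound reason for keeping them geographically apart. It does not require the arm to follow urban status.
- **Both arms share much of the pathway.** They share a screening procedure, a diagnostic centre with rapid treatment, and a city cancer registry. This narrows differences in work-up and ascertainment after screening. It does not equalise background incidence, age mix or prior screening.
- **The rejection rates rest on assumed values.** This is true, and at a ratio of 1.25 the excess over the null row is only about 2.5 percentage points by likelihood ratio and 2 by Wald. The argument does not need these rates, because the aliasing follows from the text.
- **The document is dated 2020/08/17, before recruitment began in January 2021.** Read as a plan from that date, the design could still be changed. The text, however, reports completed recruitment and a sealed database in the past tense, and the repair below relies on that.

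**Conclusion.** The concern holds. On the text as written, arm, district and urban status are one variable, the screening method was not randomly assigned, and the cluster-randomised label is unsupported. The Poisson comparison cannot attribute a difference in early cancer incidence to AI, and its interval omits between-district variance.

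The size of the bias equals the unknown background rate ratio between the two districts. The false-positive rates shown illustrate the risk for assumed ratios of 1.25 to 2.0; they are not estimates for this study. The aliasing itself needs no assumption beyond the allocation sentence and the count of two districts. Because it affects the primary comparison and the description of the design, it must be corrected.

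**What to change.** Participants and intervention states: "The database was sealed in January 2024 for analysis". The repair therefore lies in the description and the analysis.

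1. **Study population and Randomization method.** Have the sponsor confirm the allocation steps. Unless an unreported random assignment is documented, replace the design label with: a prospective non-randomised comparison of one urban district (AI-assisted ultrasound by primary health workers) and one suburban district (routine ultrasound by hospital doctors). Naming the operators matters because they also differ by arm.
2. **Statistical analysis.** Report the Poisson rate ratio, unadjusted and adjusted for age, as descriptive. Mark the age adjustment as post hoc and keep its form simple, given about 17 expected early cancers. State that the interval omits between-district variance and that the p-value supports no causal conclusion about AI.
3. **Optional sensitivity analysis.** If pre-trial age-specific incidence for the two districts can be obtained from the Shanghai registry (the documents do not show that it can), use the log of each district's expected count as the offset. Age then enters through the expected count and not again as a covariate. State that all-stage incidence is only a proxy for the early-cancer endpoint, and that this reduces the confounding without removing it.
4. **A future trial.** Randomise several districts, or smaller units, to both arms within each stratum. Limit transfer by using non-adjacent units and analysing women by district of residence. Two districts from a single stratum would remove the urban/suburban confounding but still alias arm with district.

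**Cost.** Items 1 and 2 need edits to three sections and accept a weaker claim. Item 3 needs a registry request that may fail and one extra model. Item 4 is expensive. With n districts per arm in each of two strata, the smallest possible two-sided randomisation p-value is 2/C(2n,n)²: 2/4 = 0.50 with 4 districts, 2/36 = 0.056 with 8, and 2/400 = 0.005 with 12.

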### ***Participants and intervention***

Two women and children's care centers from randomly selected two districts were the main study locations. Women in the intervention arm received AI-assisted ultrasound conducted by trained female primary health workers, while women in the control arm received routine ultrasound conducted by doctors from the Maternal and Child Health Hospital. Participants in both arms were eligible for further diagnostic evaluation and treatment at Fudan university Shanghai cancer center and women in both groups were offered access to obtain rapid treatment at the hospital. Recruitment was started in January 2021 and completed in December 2022. All participants were then followed up till the end of 2023. The database was sealed in January 2024 for analysis.

### ***Screening procedure***

Our screening procedure is based on the national Breast Cancer Screening Process Technical Guidelines issued in 2015 by the National Health Commission of People's Republic of China as follows:

(1) Clinical examination and initial breast ultrasound screening: all the participants were enrolled and received clinical examination and initial breast ultrasound or AI-assisted ultrasound. The initial screening test results were classified based on BI-RADS; (2) MG re-screening: participants with BI-RADS grade 0 or 3 were then suggested to receive MG. MG results were classified based on BI-RADS; (3) Histopathological examination (hereinafter referred to as biopsy): participants with BI-RADS grade 4 to 5 either in initial ultrasound test or MG test were suggested for further biopsy examination. For patients with MG rescreening of grade 0 or grade 3, short-term follow-up (three to six months) or further biopsy examination were suggested according to experts' evaluation; (4) Follow-up: participants with BI-RADS level 1 to 2 either in ultrasound or MG were under strict follow-up through visits and phone calls by trained medical social workers.

Final screening results (positive or negative) were based on a two-step approach. Initial screening results were determined by breast ultrasound and defined as negative with BI-RADS grade 1 or 2, positive with BI-RADS grade

4 or 5, and indeterminate with BI-RADS grade 0 or 3. Participants with indeterminate initial results were informed of the suspicious lesion detection and referred to MG assessment. The result in this second step was classified as negative or positive according to MG BI-RADS grade.

Participants receiving final negative results were exempt from additional diagnostic procedures. By contrast, those receiving final positive results were referred to Fudan University Shanghai Cancer Center for further diagnostic work-up to exclude or diagnose breast cancer. To assess interval cancers, we obtained data from all diagnosed breast cancers, plus an additional one year of follow-up from the Shanghai municipal cancer registry, one of the largest cancer registries globally, and an associate member of the International Association of Cancer Registries (IARC). For participants diagnosed with breast cancer outside of screening (ie, diagnosed with interval cancer), we collected all medical records. Two experienced radiologists reviewed the screening MG and ultrasound images from the study and the clinical MG and ultrasound images used for diagnosis of breast cancer, and reached a consensus on whether or not the breast cancer could retrospectively be identified in the screening.

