### ***Outcomes***

The primary endpoint of this study was to assess, and compare, the difference in the incidence of early breast cancer between two groups using different breast cancer screening methods (AI-assisted ultrasound screening/routine ultrasound screening). Early cancers should meet any of the following criteria at the time of diagnosis: less than 20 millimeters in diameter, no metastatic lymph nodes in the axilla, no distant metastasis, non-invasive cancers, stage 0, stage I, and stage IIA IIB (T2N1M0) breast cancer according to AJCC 8th staging.

The secondary aim was to determine the sensitivity, specificity, positive predictive value, and negative predictive value of the screening methods (AI-assisted ultrasound screening/routine ultrasound screening). Screening-detected cancers were defined as breast cancers positive for screening tests. We defined interval cancers as: breast cancers diagnosed after a negative screening test; breast cancers diagnosed after an indeterminate screening

test, but without any follow-up mammography or diagnostic examinations. A true-positive screening result was a positive result in a participant who was diagnosed with breast cancer by further diagnostic work-up. A false-positive screening result was a positive result in the absence of breast cancer. A true-negative screening result was a negative result in the absence of breast cancer and a false-negative test result was a negative result followed by diagnosis of interval cancer.

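### The plan does not say which result its accuracy figures use; on the natural two-step reading it gives no separate estimate for the ultrasound step, where the arms differ

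*Combined protocol and SAP*

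**What the plan says.** The Outcomes section gives the secondary aim as to "determine the sensitivity, specificity, positive predictive value, and negative predictive value of the screening methods (AI-assisted ultrasound screening/routine ultrasound screening"). It then builds the four accuracy counts on a positive or a negative result, for example "A true-positive screening result was a positive result in a participant who was diagnosed with breast cancer by further diagnostic work-up". It does not say at which step that result is read.

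The Screening procedure section defines results at two levels:

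- **Initial.** "Initial screening results were determined by breast ultrasound and defined as negative with BI-RADS grade 1 or 2, positive with BI-RADS grade" 4 or 5; grades 0 and 3 are a third, indeterminate category.
- **Final.** "Final screening results (positive or negative) were based on a two-step approach". "Participants with indeterminate initial results were informed of the suspicious lesion detection and referred to MG assessment", and "The result in this second step was classified as negative or positive according to MG BI-RADS grade". Women graded 1–2 or 4–5 on ultrasound keep that result.

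Women with a final positive result are the ones referred to the cancer centre for work-up (end of Screening procedure). Under Participants and intervention, the arms differ in the ultrasound method and in who performs it. One mammography rule is described for both. Neither Outcomes nor Statistical analysis specifies accuracy at the ultrasound step, or says how grades 0 and 3 would count there.

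**The concern.** A sensitivity or specificity has no clear meaning until the test result is defined. If it is the two-step result, each figure mixes the ultrasound under study with a mammography step that is not the intervention. An AI system, or an operator, that sends many more cancer-free women to mammography may show almost the same two-step specificity, because mammography clears most of them. Cancers graded 0 or 3 on ultrasound count as found or missed according to the mammogram. A difference in mammography attendance between the two districts could also move the figures.

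There is a gap in the counts as well. Mammography was only suggested, and the interval-cancer definition allows for women with an indeterminate "test, but without any follow-up mammography or diagnostic examinations". Those who later have cancer are assigned a category. Those who do not have no final result, so the plan does not say whether they enter specificity.

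**Working it through.** **Which result is meant.** The accuracy scheme has two outcomes. The initial ultrasound result has three categories and the final result has two, and final positives go to work-up. This points to the two-step result. Against it, the interval-cancer definition uses the indeterminate category, which exists by name only at the ultrasound step. The text therefore mixes levels, and the two-step basis is an inference.

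**The plan's own figures.** No accuracy figure is stated. The expected cancers (Sample size calculation) reproduce: 16,000 × 125.75/100,000 = 20.12, stated as 20; 20.12 × 0.83 = 16.7, stated as about 17.

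**Specificity.** All rates here are assumptions: d = 0.3% of cancer-free women graded 4–5; r = 5% v 15% graded 0/3; f = 5% of cancer-free referrals positive on mammography (10% as a variant); everyone referred attends.

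- Ultrasound, 0/3/4/5 positive: 1 − (d + r)
- Ultrasound, 4/5 positive: 1 − d
- Two-step: 1 − (d + r × f)

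| Result used | r = 5% | r = 15% | Gap (points) |
|---|---|---|---|
| Ultrasound, 0/3/4/5 | 1 − 0.053 = 94.7% | 1 − 0.153 = 84.7% | 10.0 |
| Ultrasound, 4/5 | 99.7% | 99.7% | 0 |
| Two-step, f = 5% | 1 − (0.003 + 0.0025) = 99.45% | 1 − (0.003 + 0.0075) = 98.95% | 0.5 |
| Two-step, f = 10% | 1 − (0.003 + 0.005) = 99.2% | 1 − (0.003 + 0.015) = 98.2% | 1.0 |

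With equal d and f in both arms, the two-step gap is f times the gap in r. In numbers of women, taking about 8,000 cancer-free women per arm (an equal split is assumed): 400 v 1,200 go to mammography, but two-step false positives are 8,000 × 0.0055 = 44 v 8,000 × 0.0105 = 84. So 800 extra referrals appear as 40 extra false positives.

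**Sensitivity.** Let a be the share of cancers graded 4–5, b the share graded 0/3, and s the mammography sensitivity among the latter. Sensitivity is a at the 4/5 cut, a + b at the 0/3/4/5 cut, and a + s × b for two-step. Assumed shares (4–5, 0/3, 1–2):

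- **Scenario A**, 70/25/5 v 50/45/5. Gap of 20 points at 4/5 and 0 at 0/3/4/5. Two-step: 82.5 − 72.5 = 10 points (s = 0.5), 87.5 − 81.5 = 6 (s = 0.7), 92.5 − 90.5 = 2 (s = 0.9).
- **Scenario B**, 60/35/5 v 60/20/20. Gap of 0 at 4/5 and 15 points at 0/3/4/5. Two-step: 77.5 − 70 = 7.5 points (s = 0.5), 84.5 − 74 = 10.5 (s = 0.7), 91.5 − 78 = 13.5 (s = 0.9).

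For equal s in both arms, the two-step gap always lies between the two ultrasound gaps. It may be much smaller than one of them, or close to it.

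**Precision.** With 10 cancers per arm (assumed), the 95% half-width for a sensitivity difference is 1.96 × √(2p(1 − p)/10): 40, 35 and 26 points at p = 70%, 80% and 90%. For specificity of 95% v 85% with 8,000 per arm, it is 1.96 × √((0.95 × 0.05 + 0.85 × 0.15)/8,000) = 0.9 points, ignoring clustering.

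**The case against.** The strongest reply is that the pathway is the right target. The primary endpoint uses the same phrase about screening methods to label the two arms, and a public programme needs to know how the whole strategy performs. Most of this stands: two-step accuracy is a legitimate estimate and should be kept. It does not provide the ultrasound-step estimate, which the wording of the aim also covers.

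A reader might infer that accuracy is computed only on the combined result, that the aim goes unanswered, and that differences between the arms are masked. The documents do not support any of these as fact. An initial ultrasound result is defined; the accuracy definitions never say which result they use; and women graded 1–2 or 4–5 keep their ultrasound result. Masking depends on unknown rates. At the 4/5 cut the illustration has no specificity gap to hide, and scenario B keeps 13.5 of 15 points at s = 0.9.

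Two further limits stand. The aim is to determine accuracy, and no test between arms is stated. An ultrasound-step contrast would still not isolate the AI, because operator and district differ too and there is one district per arm. With about 20 cancers, sensitivity is imprecise at either step. Recall and specificity use nearly all 16,000 women, and there an added estimate would tell the reader most.

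**Conclusion.** The point holds as a gap in definition with a practical consequence. The plan leaves the result behind its accuracy figures unstated. On the natural two-step reading, it has no separate estimate for the only step at which the arms differ by plan. A difference in grade 0/3 recall can then shrink in the reported specificity: from 10 points to 0.5 (f = 5%) or 1.0 (f = 10%) under the assumed rates. That comparison counts grades 0 and 3 as positive. The true size depends on the share graded 0/3 and on mammography performance and uptake, none of which the documents give. So differences can be masked; it is not shown that they are. The change is worth making, but the pathway result is not invalid without it.

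**What to change.** In Outcomes and Statistical analysis:

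1. State that accuracy based on the two-step result is the accuracy of the full screening pathway. Say on which side a mammography grade of 0 or 3 falls, and how women with an indeterminate ultrasound and no mammography are counted. Report their number by arm.
2. Add, by arm and for all screened women, sensitivity, specificity, PPV and NPV at the ultrasound step, with initial BI-RADS 0/3/4/5 as positive and again with 4/5 as positive. Use work-up plus registry follow-up as the reference.
3. State that at the 0/3/4/5 cut a cancer after an indeterminate ultrasound counts as ultrasound-positive. The present interval-cancer definition stays for the pathway analysis.
4. Use sensitivity = TP/(TP + FN) and specificity = TN/(TN + FP). The formulas now in Statistical analysis, TP/(TP + FP) and TN/(TN + FN), are those of PPV and NPV. This is a separate and more serious error, but the new table would inherit it.
5. Present arm differences descriptively, given the expected 20 or so cancers and the differences in operator and district.

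The cost is a few sentences and one more table of secondary estimates. The initial grades are recorded for every participant, so no new data are needed.
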